**Title:** Telemedicine to Improve Use of Therapeutic Hypothermia in Rural Settings

**Clinicaltrials.gov #:** NCT03706417

[figure not shown]
**Background:** Neonatal Encephalopathy (NE) is a clinical syndrome affecting between 2-5 per 1000 live births. Abnormalities in the newborn neurological exam are the hallmark of NE which occurs due to the combined effects of lack of oxygen and blood flow to the brain around the time of birth. As many as 15-20% of infants with NE do not survive their brain injury and 25% of survivors experience substantial neuro-developmental deficits including intellectual disability, cerebral palsy, epilepsy and hearing or vision loss. Until recently, infants suspected of having NE were treated with supportive care alone as there were no known therapeutic interventions. Approximately ten years ago, however, treatment options dramatically changed with the introduction of therapeutic hypothermia (TH), a novel neuroprotective therapy which involves deliberately decreasing the infant's body temperature to 33.5°C for 72 hours. The early safety studies of TH were published in the late 1990's and the positive results of the first efficacy trials in 2005 moved this promising therapy into mainstream clinical practice. In a meta-analysis of 8 published clinical trials, TH was associated with a 25% decrease in the aggregated outcome of all-cause mortality and severe neurological abnormality and, as such, has become the standard of care for these critically ill infants.

Maine Medical Center (MMC), a tertiary care center with the only Neonatal Intensive Care unit (NICU) in the southern part of the state, employed TH for the first time in 2008.

Eastern Maine Medical Center (EMMC) is the only tertiary care center in the northern part of the state and began using TH in 2009. In 2012, a Neonatal Neurology Program was started at MMC and this program was extended to EMMC through a unique and unprecedented collaboration in 2013. At both institutions, the number of infants treated with TH gradually increased with improved recognition of the mild to

moderate forms of NE (Figure 1). While educational outreach efforts have successfully increased awareness of the symptoms of NE at both tertiary care centers in the state, infants who may benefit from TH are still not always recognized in a timely fashion. Missed

Figure1: Growth in use of Therapeutic Hypothermia (TH) at MMC and EMMC.

\* Denotes partial year of data collection

opportunities for TH can occur when an infant's clinical presentation is less severe compared to those included in the original randomized controlled trials.

While TH must be initiated within the first 6 hours of life, there is solid evidence for improved outcomes in those for whom TH is initiated earlier. As a result of exceptional preclinical animal models of NE in the fetal lamb and piglet, there is a robust biochemical understanding of the temporal evolution of brain injury in neonates. TH must be initiated prior to 6 hours of life to intercede upon the second stage of injury with its features of excitotoxicity and associated cascade of inflammatory mediators that cause seizures and ultimately cell death. Animal models have demonstrated lack of neuronal rescue if TH is initiated late (8.5 hours after ischemic insult) and have also demonstrated improved neuronal rescue with earlier initiation of TH at less than 3 hours. In a prospective cohort study, infants treated with TH prior to three hours of life were found to have improved motor function compared to those whose treatment was initiated after 3 hours. In one of the first clinical trials of TH, the relative risk of death or severe abnormal neurological outcome was decreased in those for whom TH was started before 4 hours of life. This combination of animal and human data suggests that mechanisms to improve the rapid initiation of TH, such as through a teleconsult, may lead to improved outcomes for infants with NE. In the proposed study, we hypothesize that use of telemedicine consults between a tertiary care center and a community hospital can improve the assessment, management, and short-term outcomes of infants with NE by decreasing delay in the initiation of TH through rapid and accurate assessment of NE.

### **Overview of the Study Design:**

We propose to conduct a pilot intervention trial assessing the feasibility of decreasing the time to initiate TH for infants born in community hospitals who receive a Maine Neonatal Encephalopathy Teleconsult (Maine NET) compared 1:2 to with matched historical controls from the MMC database. We will also qualitatively assess provider experience of Maine NET (Appendix C) via zoom interviews and the parent perception of the process of having a telemedicine consult and participating in research in the setting of a critically ill newborn (Appendix D).

### **Study Goals:**

The goals of this study are to:

1. Utilize telehealth for Neonatal Encephalopathy consults in community hospitals to determine if telemedicine can reduce time to initiation of TH treatment

2. Capture parent experience of telemedicine consult and remote consent process
3. Capture delivery hospital clinicians' (from community hospitals and tertiary care centers) experience of utilizing telemedicine for neonatal neurological exams to assist in decision making for therapeutic hypothermia
4. Identify themes from parent and clinician experiences to identify areas of improvement for future consultations
5. Publish research findings
6. Utilize data to improve future telehealth consultations

**Human Subjects:**

Recruitment sites: Multiple community hospitals in Maine have been offered the opportunity to participate in this feasibility study and all centers have provided letters indicating a strong desire for participation. See site list for recruiting community hospitals.

Inclusion criteria: Infants in need of Maine NET will be identified by the “Time is Brain” poster (see Appendix A) that was created and distributed across the state to all newborn nurseries at community hospitals in 2016. This poster is in routine clinical use and is intended to assist in the identification of infants with symptoms of NE. Rather than having inexperienced providers at community sites examine inclusion criteria for TH and make a determination of eligibility, this poster uses a color scheme in which the green designation denotes characteristics of low-risk infants who are not in need of consultation, the yellow designation denotes characteristics of moderate risk infants who should have consultation and who may need transfer, and the red designation denotes characteristics of high risk infants who are critically ill and will benefit from immediate consultation and transfer to a tertiary care center. Infants included in this study will be born at a community hospital, will be in either the yellow or red category on the “Time is Brain” poster, will be younger than 6 hours of age at the time of the consultation. Infants in the historical control group will be selected from the MMC database and matched according to gender, gestational age, severity of presenting encephalopathy (mild, moderate or severe) and community site at which the infant was born. Matching will occur after the 35 Maine NET subjects have been treated with TH. Infants assessed by Maine NET who are not treated with TH will not be compared to the control group. The control subjects will be chosen by an investigator blinded to the time to initiate TH and outcome of the infants from the database. Infants used for historical controls must have a time of TH initiation recorded in the MMC Therapeutic Hypothermia database. Any parent of any neonate, whether treated with hypothermia or not, will be eligible to participate in an interview about their telemedicine and research experience.

Exclusion criteria: Infants older than 6 hours at the time Maine NET is requested and infants for whom TH is not an appropriate therapy (e.g. due to premature birth or moribund status) will be excluded.

Number of subjects: We intend to recruit a total of 125 infants from the participating centers. Each center has referred between 0 and 6 infants for TH annually for the past 4 years and, by involving this number centers, it is likely that the targeted goal of 125 study subjects is achievable (Table 1). We have increased the number from 10 to 20 and then to 40 and then to 100 due to the fact that not all recruited infants will be treated with TH and to have an adequate sample size to make statistical comparisons with historical controls. We anticipate that by recruiting 125 infants we will be able to analyze data in the best way possible. We will recruit no more than 30 parents for the interviews.

Power calculation: With new funding from the COBRE grant, this study has expanded to recruit 125 subjects of whom we expect 30 to have been treated with hypothermia. 30 subjects in each group would yield 95% power to detect a 1hour difference in time to initiate TH.

Informed consent: Prior to the onset of any research related activities, informed consent for the main study will be obtained from one of the infant's parents through the telehealth interface. A paper copy of the informed consent document (ICF) will be provided to the parent and will be described in full detail by [name] who will answer all the parent's questions thoroughly. The parent will then sign and date and time the ICF document if they wish to have their infant participate. Parents will be asked to initial the informed consent document if they wish to be contacted about participation in the parent interview portion of the project. The physician at the participating hospital will witness the parent signature and also sign, date and time the ICF on the witness line. [name] will then sign a separate copy of the ICF and date and time it as well. The consent form that the parent signed will be transported with the baby to MMC or faxed to MMC by providers from the community hospital and will be conjoined with the copy signed by [name] and then uploaded into the infant's electronic medical record.

If a parent chooses not to participate, [name] will thank the family for considering and the standard of care consult will occur without employing telemedicine. The current standard of care for infants born in community hospitals is to have the provider attending the delivery (pediatrician or family medicine doctor) call the NICU at MMC to describe the cord gas parameters, the Apgar scores and the level of NE in the infant as well as any other clinically relevant data. The Neonatologist at MMC may suggest that the community provider "passively cool" the newborn per our standard guideline (see Appendix B) until the transport team arrives to make the actual determination of whether the infant will require TH treatment.

Compensation: Subjects will not be compensated for participation.

Follow-up plan: All subjects treated with TH will be offered routine neurological follow up at ages 3, 6 and 12 months per usual clinical routine after treatment with TH. These follow up visits are to insure maximization of early intervention services if they are needed. These follow up appointments are part of standard clinical care.

**Primary Outcome:** Hour of life in which TH is started. The “zero hour” for TH is recorded in the infant’s electronic medical record and refers to the time at which the infant starts the TH protocol.

**Secondary Outcomes:** Time at which passive cooling is initiated, temperatures recorded by the community hospital during passive cooling, in-hospital mortality, presence of seizures on electroencephalogram (EEG) and brain injury on MRI. The EEG is a routine part of the clinical care of an infant treated with TH and is applied for the 72 hours during TH. The PI is the person primarily responsible for interpreting the results of the EEG. The MRI is also part of the routine clinical care of infants treated with TH and is interpreted by a neuroradiologist who is unaware of the status of the infant regarding whether Maine NET was utilized.

**Analysis:** Baseline differences in selected characteristics between infants assessed by Maine NET versus historical controls will be compared using Fisher’s exact tests for categorical variables and t-tests, or their non-parametric equivalents for continuous variables. The primary analysis will compare differences in the time to achieve TH between infants assessed by Maine NET versus historical controls using a t-test. For secondary outcomes of mortality, seizures on EEG, and brain injury on MRI, chi-square or Fisher’s exact test will be used for analysis of the frequency of these adverse outcomes.

**Potential limitations and contingencies:** Maine NET has been successfully locally implemented at MMC with 11 successful teleconsults already performed. There are IT and other challenges involved in implementing Maine NET at outside hospitals, but, as should be evident from the enthusiastic letters of support, these institutions are more than eager to have this level of assistance and will work collaboratively to resolve challenges. If for some reason the Maine

NET cannot happen, providers will always default to the standard of care which is a phone call for assistance with decision making.

**Potential Risks and Benefits:** When working with PHI identifiers, there is always a risk of loss of confidentiality. This risk will be minimized in this study through use of a HIPAA compliant RedCap system, limited password-protected access, and use of a Master List, which will remove all PHI identifiers from the data that is used for analysis. Interview recordings will be stored on encrypted flash drives and within the MaineHealth Protected file share folder, which only the study team has access to. All identifiers will be removed from interview transcription for analysis.

Potential benefits for this study include determining if telemedicine can reduce time to initiation of TH treatment in community hospitals as well as documenting parent and provider experience in participation in telehealth consults for neonatal encephalopathy.

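### Historical controls are not matched or limited on birth date, so the primary comparison can mix the telemedicine effect with changes in practice over calendar time.

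*Combined protocol and SAP*

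**What the plan says.** The inclusion criteria under Human Subjects state that historical controls come from the MMC database and are "matched according to gender, gestational age, severity of presenting encephalopathy (mild, moderate or severe) and community site at which the infant was born". One further eligibility condition follows: "Infants used for historical controls must have a time of TH initiation recorded in the MMC Therapeutic Hypothermia database". The person choosing controls is blinded to time to TH and to outcome. On timing, "Matching will occur after the 35 Maine NET subjects have been treated with TH". Nowhere do the documents give a birth-date window, a calendar period or a start date for the database.

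The same section identifies Maine NET infants by a poster "that was created and distributed across the state to all newborn nurseries at community hospitals in 2016".

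The Background describes practice over the years the rule leaves open. MMC "employed TH for the first time in 2008". "In 2012, a Neonatal Neurology Program was started at MMC". At both tertiary centers "the number of infants treated with TH gradually increased with improved recognition of the mild to" moderate forms of NE.

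The Analysis paragraph plans to "compare differences in the time to achieve TH between infants assessed by Maine NET versus historical controls using a t-test", with no adjustment stated. The Overview sets the ratio at one Maine NET infant to two controls.

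**The concern.** The first study goal is to learn whether telemedicine shortens time to TH. Telemedicine is expected to work through faster and more accurate assessment of NE. The poster acts on a neighbouring step, since it helps community staff recognise an infant who needs consultation. Every Maine NET infant is identified with the poster in use; a control born before 2016 could not have been.

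Matching on severity deals with case mix, so growth in the number of milder infants treated is largely covered. It does not deal with a change in how fast an infant of the same severity, at the same site, is recognised and referred. Because the primary test is unadjusted, any such change passes straight into the estimated difference in hour of life at TH start. It could create an apparent benefit or mask a real one.

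**Working it through.** **1. Does the rule permit pre-poster controls?** The conditions on a control are sex, gestational age, severity, site and a recorded TH time. None refers to date. TH at MMC dates from 2008 and the poster from 2016. So the rule permits them. How many would be chosen cannot be derived, because neither the database start date nor the birth-year distribution is given.

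**2. The plan's own figure.** The power calculation claims 95% power with 30 per group for a 1 h difference, without an SD, alpha or sidedness. It can only be solved backwards. At an assumed two-sided 5%, the noncentral t gives SD = 1.056 h (normal approximation: 1.07 h). I also use 1.5 h as a less favourable value.

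**3. Effect of era bias (illustration; drift and share are assumed).**
- Net bias b = drift × share of controls born before the poster: 0.5 h × 25% = 0.125 h; 0.5 h × 50% = 0.25 h.
- SE = SD × √(1/30 + 1/60) = 0.236 h at SD 1.056 and 0.335 h at SD 1.5.
- Rejection probability comes from the noncentral t with 88 df and noncentrality b/SE for false significance. For power when the bias opposes a true 1 h effect, the noncentrality is (1 − b)/SE.

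| Net bias | False significance, SD 1.056 | False significance, SD 1.5 | Power for 1 h, SD 1.056 | Power for 1 h, SD 1.5 |
|---|---|---|---|---|
| 0 | 5.0% | 5.0% | 98.7% | 83.9% |
| 0.125 h | 8.2% | 6.6% | 95.6% | 73.2% |
| 0.25 h | 18.2% | 11.4% | 88.1% | 59.9% |

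The inclusion criteria expect 35 treated infants, not 30. At 35 against 70 and SD 1.056, false significance is 8.7% and 20.5%, so a larger sample makes a fixed bias slightly more likely to reach significance. A simulation that also carries the extra variance from mixing two kinds of control gave similar values at 30 against 60 (7.7% and 17.2%).

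**4. Would post-poster matches be available? (assumed model)** The Number of subjects paragraph gives 0 to 6 referrals per center per year. Assume six equal sex-by-severity cells, 3 post-poster years and Poisson counts with mean = rate × 3/6, ignoring gestational age. For 30 Maine NET infants with up to two controls each, and ignoring competition for the same control:

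| Referrals per year | No candidate | Two or more | NET vs controls in a post-poster analysis | SE relative to 30 vs 60 |
|---|---|---|---|---|
| 1 | 61% | 9% | 11.8 vs 14.5 | 1.75 |
| 2 | 37% | 26% | 19.0 vs 26.9 | 1.34 |
| 3 | 22% | 44% | 23.3 vs 36.6 | 1.19 |
| 6 | 5% | 80% | 28.5 vs 52.5 | 1.04 |

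With 4 post-poster years instead of 3, the chance of two or more runs from 14% at 1 referral a year to 91% at 6.

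**5. How much does choosing the closest birth date help?** Add an assumed 8 pre-poster years at half the referral rate. Under random choice among eligible candidates, about 57% of controls pre-date the poster. Taking the closest birth dates lowers this to 52%, 43%, 34% and 12% at 1, 2, 3 and 6 referrals a year.

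**The case against.** The harm is conditional at each step. The database must reach back before 2016, early controls must actually be chosen, and speed must have changed at fixed severity and site. The documents establish none of these. The Background evidence concerns numbers treated and recognition of milder cases, which severity matching mostly absorbs, and nothing in the text says the poster shortened time to TH. The requirement for a recorded TH time might itself exclude early years. A post-2016 cut leaves later secular change untouched. The remedy is also weaker than it looks: where few candidates meet all four criteria, a closest-date rule has little to choose from. Finally, this is an openly declared historical-control pilot with a blinded selector.

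Most of this stands as a limit on weight. The drift is unknown in size and sign, and step 5 shows a small gain at low-referral sites. None of it supports leaving the date out. The rule cannot make the controls more remote in time than the present one would, and the birth-year table would show whether the issue is real. Pilot status carries limited force, because the Number of subjects paragraph says the sample was enlarged partly to support comparison with historical controls.

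**Conclusion.** The concern holds. The selection rule permits controls from before the poster, and nothing in the planned analysis corrects for it. The gap bears on the primary comparison, but it is of minor to moderate weight and does not invalidate the design. Under assumed net biases of 0.125 to 0.25 h, false significance is 7% to 18% across the two SDs. Power for 1 h falls by about 3 to 11 percentage points at SD 1.056 h and 11 to 24 at SD 1.5 h. These figures rest on a two-sided 5% test, the back-solved or assumed SD, and a drift and pre-poster share that the documents do not supply. Depending on referral rates, pre-poster controls could be common or rare.

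**What to change.** Before matching begins:

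- Add to the inclusion criteria that, among infants meeting the four matching factors, the controls with birth dates closest to the Maine NET infant's are taken.
- Report the birth-year distribution of controls with the baseline comparison.
- Add a sensitivity analysis of the primary outcome limited to Maine NET infants with post-poster controls, in 1:1 or 1:2 sets, and state how many infants drop out. Define post-poster by one fixed date, since only the year is given.
- State in the limitations that secular change after 2016 cannot be separated from telemedicine.

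I would not add birth year as a covariate. With historical controls it is nearly collinear with group, so the remedy belongs in control selection.

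The cost is protocol wording. No new patients are needed, the primary analysis loses no infant, and birth date does not reveal time to TH or outcome to the selector. The price is paid in the sensitivity analysis, whose SE is about 4% to 75% larger under the assumed model, with roughly 1 to 2 of 30 Maine NET infants dropped at 6 referrals a year and 18 at 1. At 19 against 27, power for 1 h is 87% at SD 1.056 h and 59% at SD 1.5 h. If unmatched infants come mainly from small sites, that analysis also tilts towards larger ones.

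### The only tested time outcome runs from birth against controls not matched on birth period, so an earlier call that is not due to the teleconsult would be counted as a telemedicine effect

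*Combined protocol and SAP*

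**What the plan says.** The Primary Outcome paragraph defines the endpoint as "Hour of life in which TH is started". It adds that the zero hour is held in the medical record and "refers to the time at which the infant starts the TH protocol". The Analysis paragraph states: "The primary analysis will compare differences in the time to achieve TH between infants assessed by Maine NET versus historical controls using a t-test".

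Secondary Outcomes begins with "Time at which passive cooling is initiated, temperatures recorded by the community hospital during passive cooling", without saying from what point that time is counted. The Analysis sentence on secondary outcomes opens "For secondary outcomes of mortality, seizures on EEG, and brain injury on MRI, chi-square or Fisher" and assigns no test to any time outcome.

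Both pathways start at the birth hospital. Maine NET infants are identified with the poster and a consult is then requested; Exclusion criteria removes "Infants older than 6 hours at the time Maine NET is requested". Under standard care, described under Informed consent, the local provider has to "call the NICU at MMC".

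Controls are matched on sex, gestational age, severity and birth site, and must have a recorded TH start time (Inclusion criteria). Birth period and time of call are not mentioned.

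**The concern.** Age at TH start is the sum of two parts: birth to first call or request, and call to TH start. The consult takes place in the second part. The first depends largely on recognition at the birth hospital, and the Background gives reason to think recognition has been moving. It links growing TH use to better recognition, describes outreach, and says that "infants who may benefit from TH are still not always recognized in a timely fashion". A statewide recognition poster followed in 2016 (Inclusion criteria).

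Goal 1 asks whether telemedicine shortens time to TH. With controls from an unstated earlier period and only the total compared, a shift in the first part that has nothing to do with the teleconsult looks the same as a faster process after the call. Matching on birth site limits differences between hospitals but not change over time within one. In addition, the 6-hour limit at request is stated for Maine NET infants only. This may matter little in practice, because the Background says TH itself must begin within 6 hours.

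**Working it through.** **1. The plan's own figure.** Power calculation gives 95% power for a 1-hour difference with 30 per group. It states no SD, alpha or sidedness, so the figure can only be solved backwards. Assume a two-sided t-test at alpha 0.05.

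- SE = SD × √(1/n₁ + 1/n₂); noncentrality = difference / SE; power comes from the noncentral t with n₁ + n₂ − 2 degrees of freedom.
- 30 v 30, 1 hour, 95% power: SD = 1.056 h, since 1.056 × √(2/30) = 0.273 and 1/0.273 = 3.67.
- 30 v 60 (the 1:2 ratio in Overview of the Study Design), 1 hour, 95% power: SD = 1.23 h.

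The stated 95% is attainable, but only at an SD the plan does not give. At 30 v 30 the power is 97% at SD 1.0 h, 86% at 1.25 h, 72% at 1.5 h and 48% at 2.0 h.

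**2. Effect of an earlier call alone.** Suppose nothing changes after the call, and Maine NET infants are called about d hours earlier for reasons other than the teleconsult. The mean difference in the primary outcome is then d. With 30 v 60, √(1/30 + 1/60) = 0.2236 and the critical t (88 df) is 1.987.

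| SD (h) | SE (h) | d = 0.25 h: d/SE | p<0.05 | d = 0.5 h: d/SE | p<0.05 |
|---|---|---|---|---|---|
| 1.06 | 0.237 | 1.05 | 18% | 2.11 | 55% |
| 1.23 | 0.275 | 0.91 | 15% | 1.82 | 44% |
| 2.0 | 0.447 | 0.56 | 9% | 1.12 | 20% |

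The nominal rate is 5%. Inclusion criteria speaks of 35 treated infants, not 30; with 35 v 70 and SD 1.06 h the figures are 20% and 62%. The shifts of 15 and 30 minutes are illustrations, because the documents give no call times.

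**3. Would call-to-TH time be more precise?** Take an assumed SD of 0.5 h for age at call.

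- If the two parts are independent, the call-to-TH SD is √(1.056² − 0.5²) = 0.93 h, 12% below 1.056.
- If their correlation is −0.3, the SD b solves 1.056² = 0.5² + b² − 2 × 0.3 × 0.5 × b, which gives b = 1.09 h, slightly larger than the total.

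A gain in precision therefore cannot be promised.

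**The case against.** A reader might infer that recognition was in fact faster in the study period and that the plan credits this to telemedicine. The documents do not show it. The calendar period of the controls is not given, and the poster was already in routine use, so controls may also have been born after it.

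A reader might also infer that the teleconsult cannot alter age at call, so that only a gain in call-to-TH time should be credited to it. The text points the other way. Under standard care the provider assesses the infant and then phones to describe the encephalopathy. Under Maine NET a yellow or red poster category is enough to seek consultation, and the hypothesis in the Background is that rapid, accurate assessment cuts delay. The service could lower the threshold for calling, or move assessment from before the call to after it. Call-to-TH time could then lengthen while age at TH start falls, and a strict attribution rule would reject a real benefit. Remote consent also adds a step after the call that controls lack, and call-to-TH time can itself change over calendar time. This objection stands, and the fix contains no such rule.

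The phrase about the hour of life might be read as whole-hour coding. The next sentence refers to a recorded time and no rounding is specified, so this is only wording.

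Finally, age from birth is a relevant endpoint given the 3-, 4- and 6-hour thresholds cited in the Background, and this is a pilot. Both are reasons to keep the primary outcome. Neither shows where any time was saved.

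**Conclusion.** The point holds in conditional form. The planned comparison cannot tell an earlier call from a faster process after the call, and neither matching nor any other planned analysis addresses this. Whether calls were earlier than among controls, by how much, and whether the service itself would have caused it are all unknown. The chance of a significant result with no effect after the call ranges from 9% to 18% for a 15-minute shift and from 20% to 55% for a 30-minute shift. These ranges rest on two-sided alpha 0.05, 30 v 60 infants, SDs of 1.06 to 2.0 h and assumed shifts. The sponsor should act because the issue bears directly on Goal 1 and the change is small.

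**What to change.** - Keep age at TH start as the primary outcome, and state that it is computed from the recorded birth and zero-hour times.
- Abstract the time of first call (controls) or request (Maine NET) in both groups where the records hold it. Specify this before controls are selected, which the plan places after the Maine NET infants have been treated.
- Add call-to-TH time as a secondary outcome, analysed like the primary.
- Report age at first call by group, with the number missing in each.
- State that the two intervals serve to show where any time was saved and to qualify the conclusion. Do not credit telemedicine only with the call-to-TH part.

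The cost is one extra timestamp for about 60 to 70 controls (twice 30 to 35) and a few lines in the Analysis paragraph. For Maine NET infants, age at request has to be judged against the 6-hour limit in any case, although the plan does not say that it is stored. The downside is that call times may be missing for some controls; the documents do not say they are recorded. Limiting control birth dates would reduce drift over time but would not show which interval changed.

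### Controls are matched 1:2 on four factors, but the planned t-test makes no stated allowance for the matching; the main cost is precision, with a slight bias possible if matched sets are incomplete

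*Combined protocol and SAP*

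**What the plan says.** The Overview of the Study Design describes infants who receive a teleconsult, "compared 1:2 to with matched historical controls from the MMC database". The inclusion criteria under Human Subjects say that controls are "matched according to gender, gestational age, severity of presenting encephalopathy (mild, moderate or severe) and community site at which the infant was born", and on timing: "Matching will occur after the 35 Maine NET subjects have been treated with TH".

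The Analysis section gives the primary method in one sentence: "The primary analysis will compare differences in the time to achieve TH between infants assessed by Maine NET versus historical controls using a t-test". It then turns to the binary outcomes ("For secondary outcomes of mortality, seizures on EEG, and brain injury on MRI") and names chi-square or Fisher's exact tests.

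No paired, stratified, conditional, mixed-model or covariate-adjusted analysis appears anywhere. The plan does not say whether each Maine NET infant keeps its own two controls (individual matching) or whether the control group as a whole is balanced on the four factors (frequency matching). The power statement reads: "30 subjects in each group would yield 95% power to detect a 1hour difference in time to initiate TH". It gives no SD, significance level or sidedness, and uses neither the matching nor the 1:2 ratio.

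**The concern.** Matching on factors that predict the outcome makes the two groups more alike than independent samples would be. An unmatched test still counts the variation due to those factors as error. The interval around the time saved is then wider than the data warrant, and the test rejects less often than its nominal level. The sponsor does the work of matching on four factors and may discard the precision it buys. For a pilot whose main product is an estimate of time saved, the width of that interval matters.

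A second issue arises if two controls cannot be found for every infant. Sets with two controls then weigh more in the pooled control mean than sets with one. If the number found is related to time to TH, for example through site, the simple difference in means shifts.

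**Working it through.** **Inputs from the plan.** 30 treated Maine NET infants, 1:2 matching (so 60 controls), a 1 h difference, and 95% power at 30 per group.

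**Assumptions.** Two-sided 5% level; within-set correlation rho of 0, 0.1 or 0.3; an alternative SD of 1.5 h; an alternative effect of 0.5 h. The documents give none of these.

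**Step 1: the plan's own figure.** The 95% power cannot be checked directly because no SD is given. Solving the noncentral-t power equation backwards (30 vs 30, 1 h, 95%) gives an SD of 1.056 h.

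**Step 2: standard errors with complete sets.** The matched and unmatched point estimates are identical.
- SE used by the unmatched test: 1.056 × sqrt(1/30 + 1/60) = 1.056 × 0.2236 = 0.236 h.
- True SE, used by the set-effects model: 0.236 × sqrt(1 - rho) = 0.224 h at rho 0.1 and 0.198 h at rho 0.3.
- Ratio 1/sqrt(1 - rho): 1.05 and 1.20.

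**Step 3: consequences with 30 complete sets** (simulation; unmatched t-test vs matched-set effects).

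| | rho 0 | rho 0.1 | rho 0.3 |
|---|---|---|---|
| Type I error, unmatched | 4.9% | 3.8% | 2.0% |
| 95% CI half-width, SD 1.056 h | 0.47 vs 0.47 h | 0.47 vs 0.45 h | 0.47 vs 0.39 h |
| Power for 1 h, SD 1.056 h | 98.7% vs 98.6% | 99.1% vs 99.3% | 99.6% vs 99.9% |
| Power for 0.5 h, SD 1.056 h | about 55% for both | 56% vs 59% | 57% vs 70% |
| Power for 1 h, SD 1.5 h | 84.0% vs 83.7% | 85% vs 87% | 88% vs 94% |

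The set-effects model holds its type I error at 4.9% to 5.0%. A closed-form check with the noncentral t gives the same set-effects power (59% and 70% for 0.5 h).

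**Step 4: frequency matching** (30 vs 60, 8 assumed sites, matching factors explaining a share R² of the variance). At R² 0.3 the unadjusted type I error is 2.3%. The half-width is 0.46 h unadjusted, 0.43 h adjusted for severity, gestational age and gender, and 0.39 h with site added. Power for 0.5 h is 58%, 65% and 70% respectively. The loss is about the same as with individual sets.

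**Step 5: incomplete sets.** The power section says: "Each center has referred between 0 and 6 infants for TH annually for the past 4 years". At small centers a second control who also matches on the other three factors may not exist. Take the extreme case in which the half of sets with longer expected times find one control and the other half find two. The mean set effect in each half is ±m, with m = sqrt(rho) × 1.056 × sqrt(2/π). The control mean then shifts by (0.5 × 1 × m - 0.5 × 2 × m)/1.5 = -m/3.
- rho 0.1: m = 0.266 h, shift 0.09 h.
- rho 0.3: m = 0.461 h, shift 0.15 h.

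Simulation at rho 0.1 to 0.3 gives about 0.06 to 0.15 h when the association is strong or extreme, and 0.04 to 0.08 h when it is moderate. The sign depends on which sets lose a control. Type I error of the unmatched test stays below 6% (at most about 5.5% in the check run for this note). With fixed set effects the bias is nil within simulation error.

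**The case against.** The strongest defence is that nothing fails at the plan's own values: power is at least 98% with or without the matching, the study is a pilot, and a simple unadjusted test after matching errs on the cautious side. That stands, and it is why the point is minor.

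Second, the plan does not say that the t-test is unpaired. A one-sample t-test of each infant against the mean of its own controls would also be a t-test. This also stands in part. The fair charge for the primary outcome is that no allowance for the matching is stated, not that an unmatched test was knowingly chosen.

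Third, the size of the loss rests on assumed inputs. A material loss (57% vs 70%) needs both rho 0.3 and half the planned effect. With half the sets incomplete and rho 0.1, set effects gain only 1 to 2 points, and the test against own-control means gains about nothing. The frequency-matching result assumes controls that closely reproduce the joint distribution of site, severity and gender; looser matching was not examined. Nor is 1.5 h a firm ceiling for the SD. The Background says "While TH must be initiated within the first 6 hours of life", and a uniform spread over 0 to 6 h has SD 6/sqrt(12) = 1.73 h, but the eligibility limit applies to age at consultation, not at TH start.

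A reader might infer that ignoring the matching produces false positives or leaves the study underpowered. The documents support neither. With complete sets the error rate falls below 5%, and even under extreme incomplete matching it rises only slightly above. At the stated effect and implied SD, power is ample.

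**Conclusion.** The point holds and is minor. The plan matches on four factors and states no use of them in the analysis.

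With complete sets of distinct controls and non-negative rho, an unmatched t-test is unbiased but has a standard error 5% too large at rho 0.1 and 20% too large at rho 0.3. Nothing is lost at rho 0. The cost is interval width, and power if the effect is smaller or the SD larger than planned.

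It would go too far to call the unmatched test valid whatever the matching yields. If some infants find one control and that is related to time to TH, the difference can be off by about 0.06 to 0.15 h at rho 0.1 to 0.3, which is small beside the planned 1 h. These figures concern the matching alone; they say nothing about bias from using historical controls, inexact matches or controls reused across sets.

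**What to change.** In the Analysis section, state whether matching is individual or by frequency, and make the primary analysis follow from it:
- **Individual:** a linear model for hour of life at TH start with matched-set effects. Fixed effects also remove the incomplete-set bias shown above.
- **Frequency:** a linear regression adjusted for severity, gestational age, gender and, where numbers allow, site.

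In either case report the mean difference with its 95% CI, and keep the unmatched t-test as descriptive. Controls are chosen only after 35 infants have been treated, so this can be settled before any are selected.

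A set-stratified analysis (Mantel-Haenszel or exact conditional) of mortality, EEG seizures and MRI injury is optional. Only discordant sets contribute, so it helps only if events are frequent enough.

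**Cost.** Wording only; no new data or patients. If the matching factors do not predict time to TH, set effects cost under 0.5 point of power with complete sets (84.0% vs 83.7% at SD 1.5 h and 1 h) and about 2 points with half the sets incomplete (79.9% vs 78.2%). The adjusted regression costs at most 1 point (55.7% vs 54.7%).
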